B3. We will leverage existing health system technologies and partnerships with public agencies to develop an infrastructure to ensure accountability in the equitable allocation of COVID-19 vaccines to children. By linking pre-registration for the COVID-19 vaccine to information about the child's demographics and health in the Nemours EHR, we will be providing easy registration for families from a trusted source, removing many of the barriers experienced with current registration systems. The EHR-linked registry that will be created will be available to the Nemours primary care network and partners at the Delaware Division of Public Health to ensure that COVID-19 vaccine allocation and distribution to children matches demand when it becomes available and to track any inequities in vaccine delivery in real-time, allowing for continual improvement in our efforts to ensure equitable COVID-19 vaccination among all children in Delaware.¹⁷

C. APPROACH

C1. OVERVIEW. The proposed study will develop and test a multi-component intervention to improve COVID-19 vaccine uptake among pediatric populations in underrepresented communities in Delaware. An intervention will be developed using best-practice community-based participatory research methods (Aim 1). The intervention will be refined in an iterative process using innovative crowdsourcing methods with Black and Latino youth and caregivers (Aim 2). The intervention will be pilot tested in a cluster randomized controlled trial with four primary care practices in Delaware and the communities they serve (Aim 3). **Overall project goal:** We will develop a culturally-tailored, community-informed approach to increase pediatric COVID-19 vaccine uptake among Black and Latino communities.

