INTERVENTION REFINEMENT: Ratings on the AIM range from 1 to 5, with higher scores indicating greater acceptability. A score of 4 indicates that participants "agree" that interventions are acceptable. Intervention components with a mean score < 4 will be modified based on qualitative responses, with the research team determining what modification can be made based on importance and feasibility. The process of revision and participant feedback will continue until the mean acceptability score is ≥ 4 .

AIM 3. Test the preliminary efficacy of the intervention through a pilot cluster randomized controlled trial of the intervention at 4 Nemours primary care sites.

[figure not shown]
PARTICIPANTS: Four primary care practices will be enrolled in the study (Figure 4), leveraging RPL [name]'s prior work with primary care practices in Delaware and co-I's [name] role as Director of the Nemours Primary Care Network. The four primary care practices selected for the study have large and diverse patient populations, with two practices in Northern Delaware (Becks Woods, Foulk Road) and two in Southern Delaware (Milford, Seaford) having comparable patient demographics. All practices are within the Nemours Children's Health System, which provides care to the majority of children in the state, and share an EHR.

STUDY DESIGN: A pilot cluster randomized controlled trial will be conducted, with clustering at the practice level. Enrolled practices will be randomly allocated to receive the intervention (Intervention Practice) or not (Control Practice) using a 1:1 randomization scheme stratified by practice location (Northern or Southern Delaware).

OUTCOME MEASURES

Vaccination Rates: We will extract EHR data about rate of COVID-19 vaccination for all eligible children at each practice.

Accountability for Vaccination: Vaccination rates for each site will be made available and reviewed monthly by the Nemours Primary Care

Network, who will share an overview of de-identified data with the Delaware Division of Public Health and partner with them to ensure that enough COVID-19 vaccines will be allocated and distributed to communities to meet demand and that continual efforts to encourage vaccination.

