Disparities: Child race/ethnicity (Black, White, Latino, Other) will be the primary measure of disparity and will be collected from the EHR. Zipcode from the EHR will be used to categorize patients into rural vs. not (RUCA ≥4)⁴⁰ and to generate a Child Opportunity Index score⁴¹ for each child as secondary measures of disparity. Insurance, sex, medical diagnoses, and caregiver preferred language will also be collected from the EHR.

ANALYSES: Analyses demonstrated the efficiency of the stratified cluster randomized trial in detecting a difference in vaccination rate of 30% among Blacks in the Control Practices compared to an increase in vaccination rate to 60% among Blacks in Intervention Practices, with a sample size of 500, $\alpha < 0.05$ and power of 90%. Proportions of caregivers who vaccinate their child will be compared by level of intervention using chi-square tests. To test the efficacy of the intervention, while accommodating the cluster-randomized design of the study, a multi-level mixed-effects model (MME) logistic regression will be used fit to the data for the primary outcome of child vaccination rate to assess the effect of intervention. MME models will be adjusted for race/ethnicity to evaluate the effect of intervention on reducing this disparity.

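### The 90% power is stated for Black children only and is not shown for the primary test, which is described over all eligible children

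*Combined protocol and SAP*

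**What the plan says.** All of this is in the Combined protocol and SAP, section C4, Aim 3, unless noted.

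- **Power (Analyses).** The trial is sized for a "difference in vaccination rate of 30% among Blacks in the Control Practices compared to an increase in vaccination rate to 60% among Blacks" in the intervention practices, "with a sample size of 500", alpha 0.05 and 90% power. The text does not say whether 500 counts Black children or all children, or whether it is a total or a per-arm number. It gives no intracluster correlation (ICC).
- **Outcome (Outcome Measures).** The EHR extract covers the "rate of COVID-19 vaccination for all eligible children at each practice".
- **Primary model (Analyses).** The mixed-effects logistic regression is fitted "for the primary outcome of child vaccination rate to assess the effect of intervention". No restriction by race is stated. Race/ethnicity (Black, White, Latino, Other) enters as an adjustment variable, which implies that several groups are in the model.
- **Goal (C1 Overview).** The project aims at a tailored "approach to increase pediatric COVID-19 vaccine uptake among Black and Latino communities".
- **Clusters (Participants).** "Four primary care practices will be enrolled in the study", randomised 1:1 within region, so two per arm.

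No power is given for all children, for Latino children, or for a difference in effect between race groups.

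**The concern.** The trial is sized on one population and its primary test is described on another. With race as a main-effect covariate only, the intervention coefficient is a weighted average over Black, Latino, White and Other children. It does not isolate the effect in Black children on which the sample size rests.

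If the tailored intervention helps mainly the groups it was designed for, the averaged effect is smaller than 30 points. A narrowing of the disparity in fact requires a smaller gain in the comparison groups. The primary test could then miss an effect of the size the trial was planned around. This matters even for a pilot, because Aim 3 sets out to test preliminary efficacy and section C7 uses the result to support a larger trial.

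**Working it through.** **1. Inputs.** From the plan: 30% and 60% (Black children), 500, alpha 0.05, 90%, four practices. Assumed: two-sided test and 500 as a total (250 per arm, 125 per practice). Race mix: the practices' own mix is not given, so the Table 1 survey totals (A.3) stand in for it. These are Latino 94 + 17 + 56 = 167, Black 98 + 47 + 125 = 270, White 869, Other 193, total 1,499. Black is 270/1,499 = 18.0% and Latino 167/1,499 = 11.1%.

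**2. Formula.** With n per arm, d = p2 − p1 and p̄ the mean of p1 and p2:

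power = Φ{ [d − 1.96·√(2p̄(1−p̄)/n)] / √([p1(1−p1) + p2(1−p2)]/n) }.

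Clustering is added by replacing n with n / [1 + (m − 1)·ICC], where m is the number of children per practice. This crude comparison approximates the adjusted logistic model. The normal approximation is optimistic with two practices per arm.

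**3. The plan's own figure.** For 30% vs 60% with n = 250: [0.30 − 1.96 × 0.0445] / 0.0424 ≈ 5.0, so power is above 99.9% without clustering. A power of 90% needs only 56 per arm. The stated 90% with 500 in total therefore implies an unstated design effect of about 4.49, that is an ICC of (4.49 − 1)/124 ≈ 0.028. The figure can be matched in this way but not verified.

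**4. All-children difference if only the named groups gain 30 points.**
- Black only: 0.180 × 30 = 5.4 points.
- Black and Latino: (0.180 + 0.111) × 30 = 8.7 points.

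**5. Unclustered power for that difference, control rate 45% or 30% (assumed).** Worked example, 45% vs 50.4% with n = 250: [0.054 − 1.96 × 0.0447] / 0.0446 = −0.75, and Φ(−0.75) = 0.23.

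| Meaning of 500 | Children in primary test | 5.4 points | 8.7 points |
|---|---|---|---|
| All children | 500 (250 per arm) | 23-25% | 49-54% |
| Black children only | 500/0.180 ≈ 2,776 (1,388 per arm) | 81-86% | above 99% |

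On the first reading about 90 children are Black (45 per arm). Power for 30% vs 60% in them is then 83% before clustering.

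**6. Effect of clustering.** As m grows, the effective n per arm tends to 2/ICC. At the back-solved 0.028 that is about 71 per arm however many records are extracted. Power is then at most about 10% for 5.4 points and 18-19% for 8.7 points.

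**7. If other groups also gain.** Control rates here are 30% for Black children and the Table 1 yes share for the others, which gives 52.8% overall. There are 500 children in total.

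| Assumed gain | Overall | ICC 0 | ICC 0.01 | ICC 0.028 |
|---|---|---|---|---|
| Black +30 | 5.4 | 23% | 13% | 8% |
| Black and Latino +30 | 8.7 | 51% | 26% | 15% |
| Same, others +10 | 15.8 | 95% | 68% | 40% |
| All groups +30 | 30 | >99% | >99% | 93% |

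Only the last row keeps about 90% at the ICC that reproduces the plan's figure.

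**The case against.** The strongest reply is that the low power figures come from assumptions outside the plan, and much of it stands.

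- **Sample size.** Nothing caps the primary dataset at 500, and the extract covers every eligible child at practices described as large. On the reading that 500 counts Black children, the unclustered figures are high. This stands, although step 6 shows that more records per practice help little once there is meaningful clustering.
- **Race mix.** Table 1 is a caregiver survey, not these four practices. At 40% Black and 30% Latino the gains would be 0.40 × 30 = 12 and 0.70 × 30 = 21 points, with unclustered power at 500 of about 77-80% and above 99%. This stands.
- **Zero effect elsewhere.** Example components such as practice flyers, vaccine registration and an EHR dashboard could reach families of any race. This stands.
- **Unseen source.** C4 refers to a separate PHS form for the sample size justification. It is not among the documents and may define 500 or give an ICC.

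A reader might infer that the primary test is underpowered, or that no such power exists. The documents do not support this, since the results above run from about 8% to above 99%. A reader might also infer that a null result will be reported as a failure at 90% power. The plan ties the 90% to a contrast in Black children and never claims it for the mixed model, so that is a risk of misreading and not something the plan says.

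None of this removes the mismatch: the power inputs name one group, and the primary model as written does not.

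**Conclusion.** The point holds as a gap in what the plan demonstrates. The 90% belongs to a contrast in Black children that no described test isolates, and no power is given for the primary test that is described. That the model covers all children is read from the outcome definition and the race/ethnicity adjustment, because the model sentence does not itself name its population.

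The size cannot be fixed from the documents. The 23-25% and 49-54% figures hold only under all four assumptions together: Table 1 mix, gain confined to the named groups, 500 children in total and no clustering. Changing what 500 counts is enough to move them to 81-86% and above 99%, before clustering reduces them again. The plan should correct this before analysis. It is not evidence that the trial cannot succeed.

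**What to change.** State what 500 counts (which children, total or per arm), and do not attach the 90% to the all-children test. Then do one of the following:

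1. Keep all eligible children as primary. Restate power for that test from the practices' actual race mix and sizes, a stated effect in each race group and a stated ICC.
2. Pre-specify the intervention effect in Black children, estimated from an intervention-by-race/ethnicity term in the same model, as the contrast to which the power statement refers. Give the ICC behind the 90%.

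Restricting the primary set to Black and Latino children would suit the stated goal, but it is partly a matter of preference. It would still not match power inputs that are for Black children only, and White children are needed for the disparity comparison.

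The cost is SAP wording and one recalculation, using practice counts from the EHR. No extra participants are needed. The stated power may become less favourable.

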Officer for Nemours Children's Health System; **2) [name], MPH**, Director of the Christiana Care Harrington Value Institute Community Partnership Fund and Harrington Trust Physician Scholar; **3) [name]**, Director of the University of Delaware (UD) Partnership for Healthy Communities and Professor of Practice and Distinguished Health and Social Services Administrator; and **4) [name]**, Attending Physician in the Nemours Division of Infectious Disease to provide expertise on the public health response to the pandemic. Finally, this project leverages robust resources offered by the Nemours Primary Care Network (Director **[name]**, co-investigator), and the Nemours Office of Health Equity and Inclusion (Research Associate **[name], BSPH, MPH**, co-investigator). Nemours Marketing and Center for Health Delivery Innovation (CHDI) will help create intervention prototypes and final intervention components.

C3. PARTNER ENGAGEMENT PLAN. To create a culturally-tailored and community-informed intervention, community and healthcare stakeholders (Table 2) will be engaged as research partners. Identification and engagement of partners will be facilitated by the UD Partnership for Healthy Communities ([name]) and Harrington Value Institute Community Partnership Fund ([name]). This Council of Community and Healthcare Partners will meet regularly throughout the course of the study with our team of investigators. Best practices from the Promising Practices Guide developed by the University of New Mexico's Engage for Equity team will be followed to ensure that community partner engagement is successful.¹⁷⁻²⁰ In addition, three FYREworks training modules²¹ (30 minutes each) will be completed by all community and healthcare partners prior to the first meeting to foster an understanding of their role in the research process.^{18,20} The quality of the research partnership will be evaluated using Engage for Equity's Community Engagement Survey²⁰ following every meeting to ensure partner synergy and alignment of values, modifying our community engagement practices as needed based on responses.

C4. STUDY DESIGN. Please see PHS Human Subjects & Clinical Trials form for detailed eligibility criteria, sample size justification, recruitment/retention plan, timeline, human subjects protection, participant compensation, and data/safety monitoring.

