C6. SCIENTIFIC RIGOR. This study was designed to ensure that it will yield robust results. We are involving community partners throughout the project and using empirically supported practices to engage community partners as members of the research team and co-create the intervention for this study.⁴² In addition, we will repeatedly evaluate the quality of community partner engagement using well-validated measures that are associated with both intermediate and distal outcomes of community-academic partnerships²⁰ and will modify engagement strategies based on these data to ensure high quality partner engagement. The planned sample size for crowdsourcing is based on experience from similar studies^{36,37} and we are using well-validated instruments and rigorous qualitative methodology to assess the acceptability and feasibility of the intervention components. We will test the co-created and refined intervention in a cluster randomized controlled trial for maximum impact and have chosen primary care practices because of the large and diverse communities they serve. Finally, rigorous data analytic approaches and transparent reporting guidelines will be followed.

C7. FUTURE DIRECTIONS AND SUSTAINABILITY. This project will result in a community-informed intervention to increase COVID-19 vaccine uptake among Black and Latino children and provide preliminary evidence of the efficacy of the intervention. Because the intervention is integrated into existing Nemours infrastructure and leverages Nemours resources, it will be readily available for use more broadly across the entire Nemours Children's Healthcare System once the study is complete, contributing to the sustainability of the project and its intended impact. The results from this project will also position the research team to apply

Table 5. Study Timeline

	Jul-Sep	Oct-Dec	Jan-Mar	Apr-Jun
Research Partner Meetings				
Co-Develop Intervention (Aim 1)				
Conduct Crowdsourcing (Aim 2)				
Finalize Intervention (Aim 2)				
Pilot Cluster RCT (Aim 3)				
Data Analysis & Dissemination				

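### The 90% power stated for Aim 3 (30% vs 60%, sample size 500) is supported with two practices per arm only if between-practice variation is small

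*Combined protocol and SAP*

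**What the plan says.** In section C4, Aim 3, the Analyses paragraph sets 30% among Black children in control practices against "an increase in vaccination rate to 60% among Blacks in Intervention Practices, with a sample size of 500", at alpha 0.05 "and power of 90" per cent. It credits this to the stratified cluster design.

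Under Participants, "Four primary care practices will be enrolled in the study". Under Study Design, practices are allocated "using a 1:1 randomization scheme stratified by practice location (Northern or Southern Delaware". That gives two practices per arm, one per arm in each location.

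For the analysis, "a multi-level mixed-effects model (MME) logistic regression will be used fit to the data for the primary outcome of child vaccination rate". The plan does not state the reference distribution for the intervention test, the ICC, the sidedness, or whether 500 counts Black children only or all children, and in total, per arm or per practice.

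Section C4 opens by sending the reader elsewhere: "Please see PHS Human Subjects & Clinical Trials form for detailed eligibility criteria, sample size justification". That form is not among the supplied documents.

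The framing is modest. Aim 3 is to "Test the preliminary efficacy of the intervention through a pilot cluster randomized controlled trial", and section C7 expects the project to "provide preliminary evidence of the efficacy of the intervention" ahead of a larger cluster trial.

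**The concern.** With two practices per arm, the variation between practices in the same arm is estimated on 4 - 2 = 2 degrees of freedom, or on 1 if location is also fitted. A power figure that treats this variation as known, or as nearly absent, can be far too high. A test that does the same can reject far too often.

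This is the only power statement for Aim 3 in the supplied text, and it is unqualified. If it stands, a null result could be set against a 90% that the design is not shown to have. A nominally significant result from an uncorrected model could also lend unearned support to the larger trial.

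**Working it through.** **Inputs.** From C4, Aim 3: rates 0.30 and 0.60, sample size 500, alpha 0.05, four practices. Assumed here: 500 is the total, so m = 125 children per practice; practices are of equal size; ICC runs from 0 to 0.05. No ICC comes from the documents.

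**Step 1: the plan's own figure.** Ignoring clustering, 250 per arm gives power above 99.99%, and 90% needs only 56 per arm two-sided (46 one-sided). So the stated inputs alone do not yield 90%. With a design effect at ICC 0.03:
- Design effect = 1 + 124 × 0.03 = 4.72; effective sample size = 500/4.72 = 105.9.
- Var(difference) = (0.21 + 0.24) × (ICC + (1 - ICC)/m)/2 = 0.45 × (0.03 + 0.97/125)/2 = 0.0085; SE = 0.0922.
- Ratio = 0.30/0.0922 = 3.25. Normal-reference two-sided power = Φ(3.25 - 1.96) = 90.2%.

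The stated 90% can therefore be matched at an ICC of about 0.03 if the between-practice variance is taken as known. It can also be matched by a two-sided practice-level test on 2 df at an ICC near 0. Which route was used, if either, is not known.

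**Step 2: practice-level t test.** Same SE, with power from the noncentral t and noncentrality 0.30/SE. The two-sided critical value on 2 df is 4.303.

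| Assumed ICC | 0 | 0.01 | 0.03 | 0.05 |
|---|---|---|---|---|
| SE | 0.0424 | 0.0635 | 0.0922 | 0.1138 |
| Noncentrality | 7.07 | 4.72 | 3.25 | 2.64 |
| Normal reference, two-sided | 100% | 99.7% | 90.2% | 75.0% |
| t on 2 df, two-sided | 91.7% | 68.0% | 43.3% | 32.3% |
| t on 2 df, one-sided | 99.2% | 89.2% | 67.1% | 53.5% |
| t on 1 df, two-sided | 42.1% | 28.9% | 20.2% | 16.4% |
| t on 1 df, one-sided | 73.1% | 54.0% | 38.9% | 32.0% |

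On 2 df, 90% holds up to an ICC of about 0.0007 two-sided or 0.009 one-sided. The 1-df rows assume that fitting location removes no variance.

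**Step 3: the planned model.** Simulation with four practices, beta-distributed practice rates, m = 125, a random-intercept logistic model with the intervention term only, and 10,000 trials per scenario. Two-sided unless stated.

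| Assumed ICC | 0.01 | 0.03 | 0.05 |
|---|---|---|---|
| Type I error, Wald z | 14.0% | 22.0% | 26.8% |
| Type I error, likelihood ratio | 10.7% | 16.2% | 19.1% |
| Type I error, t on 2 df | 0.2% | 1.9% | 3.7% |
| Power, Wald z | 99.6% | 93.7% | 85.7% |
| Power, likelihood ratio | 98.5% | 87.2% | 76.3% |
| Power, t on 2 df | 82.1% | 58.0% | 44.3% |
| Power, t on 2 df, one-sided | 96.5% | 81.1% | 68.1% |
| Power, Wald cut-off tuned to 5% at the true ICC | 97.9% | 71.9% | 48.6% |

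Smaller separate runs put the Wald type I error at ICC 0.03 at up to about 25%. With t on 2 df, two-sided power is 90.5% at ICC 0.005 and 89.8% at 0.0055 (20,000 trials each).

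**Step 4: what the ICCs mean.** The between-practice SD is √(ICC × p(1 - p)). At ICC 0.03 it is √(0.03 × 0.21) = 0.079 to √(0.03 × 0.24) = 0.085, about 8 percentage points. At ICC 0.005 it is √(0.005 × 0.21) = 0.032 to √(0.005 × 0.24) = 0.035, about 3 points.

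**Step 5: more children.** At ICC 0.03, practice-level two-sided power on 2 df is 46.6% if 500 is per arm and 48.4% if it is per practice. With unlimited children, Var = 0.45 × 0.03/2 = 0.00675, noncentrality = 0.30/0.0822 = 3.65, and power is 50.4%.

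**The case against.** **The ICC is assumed.** This stands. The value 0.03 has no source in the documents. One health system, a shared record, stratification by location and similar patient demographics could all keep residual variation small. At ICC 0.01 the planned model on 2 df has 82% power two-sided and 96.5% one-sided. Part of the two-sided shortfall there is conservatism of the t reference, since a cut-off tuned to the true ICC gives 98%; but that ICC would have to be known in advance.

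**The practice-level t test is not the planned analysis.** This also stands. A reader might infer that true power is 43%. The documents do not support that: it is one ICC, two-sided, for a different test. The planned model on 2 df gives 58% two-sided and 81% one-sided at the same ICC.

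**The missing form may answer part of this.** It may give the ICC, the sidedness and what 500 counts, so their absence from the supplied pages is not in itself a fault. It cannot add practices.

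**It is a pilot.** The framing limits the consequence, and nothing in the plan says a null result would be read as no effect. But the framing does not withdraw the 90%.

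**Conclusion.** The point holds as an unsupported power statement. Two-sided, the planned model on 2 df supports 90% up to an ICC of about 0.005, a between-practice SD of about 3 percentage points. One-sided, the limit lies between ICC 0.01 (96.5%) and 0.03 (81.1%). At ICC 0.03 no two-sided test checked that holds alpha reaches 90%. These figures rest on assumed ICCs, equal practice sizes and 500 as the total. The last matters little at ICC 0.03, where the limit is the number of practices.

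Three stronger readings should be resisted. A reader might infer an arithmetic slip, or that clustering was ignored; the derivation is not shown, and 90% can be matched by a design-effect calculation. A reader might infer that the pilot needs more practices; its stated purpose is preliminary, and only the claim about power is out of line. A reader might also want a fixed forecast of interval width. At ICC 0.03 the practice-level formula gives 4.303 × 0.0922 = 39.7 points, but the simulated median half-width is about 33 and the middle half runs from about 21 to 47. Those figures are for a risk difference, not for the planned logistic model. The issue should be fixed, but it does not undermine the pilot.

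**What to change.** In section C4, Aim 3, Analyses:

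1. Replace the unqualified 90% with power for the planned model over a stated ICC range. Give the sidedness, the degrees of freedom, and what 500 counts (Black or all children; total, per arm or per practice). Carry these over from the cited form if it gives them; otherwise state them.
2. Name a small-cluster reference for the intervention test, such as t on 2 df (1 df if location is fitted), in place of an uncorrected Wald or likelihood-ratio test.
3. In keeping with the pilot framing, do not describe Aim 3 as a 90%-powered efficacy test. Report the effect with its interval, and say in advance that the interval will be wide and its width unstable, without a fixed figure.

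The change is to wording and to the named test; no patients or practices are added. The cost is a less favourable stated power and a reference that is conservative when the ICC is small (simulated type I error 0.2% at ICC 0.01).

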DATA COLLECTION: Crowdsourcing is a form of online problem-solving in which a problem or question is presented to a group of individuals with relevant experiences and perspectives to solicit pertinent and timely input.³⁰ Crowdsourcing has been used extensively to conduct research on health behaviors.³¹⁻³³ Yammer, a secure collaboration tool that resembles social media sites familiar to most participants, will be used for crowdsourcing. Intervention components (e.g., videos, registration websites) will be posted to Yammer. Participants will be able to view or engage with the intervention components through the platform and will rate the acceptability of each intervention component on the AIM. In addition, participants will be asked to provide feedback via Yammer on why they felt that intervention components were or were not acceptable. Participants will be able to post free-text responses to queries and see others' responses. This simulates participant interactions found in focus groups while reducing logistical barriers to participation (e.g., travel, coordinating schedules), which will facilitate inclusion of healthcare providers and socioeconomically disadvantaged families. Participants will be given the option of completing an electronic survey or qualitative interview with the same questions posed to the online crowds if they feel uncomfortable posting on Yammer. Participants will be compensated, via Greenphire, for each AIM rating and each free-text response. Participants can earn up to \$120 once this portion of the study ends, based on number of responses and ratings completed.

ANALYSIS: Quantitative data (AIM ratings) will be analyzed via descriptive statistics. Qualitative data (free-text responses) will be analyzed using an inductive thematic approach (Table 4). Data will be analyzed until code and meaning saturation has occurred and the findings are reliable and thorough.³⁴⁻³⁷ Quantitative and qualitative data will be mixed through the process of *building*^{38,39} in which qualitative data are used to provide a more thorough understanding of participants' ratings of acceptability (e.g., codes can be stratified to explore whether different themes emerge for participants based on acceptability ratings).

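### The planned between-arm chi-square tests ignore randomisation by practice, so their p-values are too small if practices within a location differ

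*Combined protocol and SAP*

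**What the plan says.** All of this is in section C4 of the combined protocol and SAP.

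- **Aim 3, Study Design:** "A pilot cluster randomized controlled trial will be conducted, with clustering at the practice level". Allocation is 1:1 within location, so each arm receives one northern and one southern practice.
- **Aim 3, Participants:** "The four primary care practices selected for the study have large and diverse patient populations", and they are described as "having comparable patient demographics".
- **Aim 3, Outcome Measures:** the outcome taken from the health record is the "rate of COVID-19 vaccination for all eligible children at each practice", which is child-level data on everyone eligible.
- **Aim 3, Analyses:** "Proportions of caregivers who vaccinate their child will be compared by level of intervention using chi-square tests". No adjustment for practice or location is stated, and the tests are not called descriptive, unadjusted or exploratory. The next sentence opens "To test the efficacy of the intervention, while accommodating the cluster-randomized design of the study" and assigns the primary outcome to a mixed-effects logistic model. Nothing says which result governs if the two disagree.
- **Aim 2, Analysis:** where the plan intends description only, it says so: "Quantitative data (AIM ratings) will be analyzed via descriptive statistics".

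**The concern.** The unit of randomisation is the practice, but the chi-square test takes the child (or caregiver) as the independent unit. With one intervention and one control practice in each location, whatever makes those two practices differ apart from the intervention enters the arm contrast directly. The chi-square standard error has no term for it. The test can therefore show a significant arm difference when the intervention did nothing.

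That p-value would concern the same outcome as the mixed model. Section C7 says the pilot is meant to supply early evidence that the intervention works and to support an application for a larger trial. A p-value that is too small, set beside the model result, could overstate that evidence.

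**Working it through.** **1. The plan's own figure.** The Analyses paragraph gives 30% versus 60%, N = 500, alpha 0.05 and 90% power. For two independent proportions, two-sided, with mean proportion 0.45:

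n per arm = [1.96·√(2·0.45·0.55) + 1.2816·√(0.30·0.70 + 0.60·0.40)]² / 0.30² = (1.379 + 0.860)² / 0.09 ≈ 55.7, so 56 per arm and 112 in total.

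Independence therefore does not give 500. If 500 is the total, the practices are equal (125 each), the test is two-sided and a standard design effect was used, the implied design effect is 250/55.7 = 4.49 and the implied ICC is (4.49 − 1)/124 = 0.028. This is not shown to be an error in N: section C4 refers the sample size justification to a form that is not among the documents. The value 0.028 serves below only as one point in a range.

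**2. Error rate of the chi-square test under no effect.** Assumptions: 30% vaccinated in both arms, nominal two-sided 5%, m children per practice, and ICC measured between practices within a location.

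Design effect DE = 1 + (m − 1)·ICC; actual error ≈ 2·[1 − Φ(1.96/√DE)]; practice SD = √(ICC·0.3·0.7).

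For m = 125 and ICC 0.01: DE = 1 + 124·0.01 = 2.24, 1.96/√2.24 = 1.31, error ≈ 19.0%. The simulations used 400,000 trials per cell, beta-binomial practices, one northern and one southern practice per arm, and Pearson chi-square without continuity correction.

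| ICC | Practice SD (points) | DE, m = 125 | Formula | Simulated |
|---|---|---|---|---|
| 0.001 | 1.4 | 1.124 | 6.4% | 6.5% |
| 0.005 | 3.2 | 1.62 | 12.4% | 12.3% |
| 0.01 | 4.6 | 2.24 | 19.0% | 19.1% |
| 0.028 | 7.7 | 4.472 | 35.4% | 35.8% |
| 0.05 | 10.2 | 7.2 | 46.5% | 47.0% |

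**3. Practice size.** The documents give none, so these sizes are assumed. Simulated error at the same five ICCs:

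| m | 0.001 | 0.005 | 0.01 | 0.028 | 0.05 |
|---|---|---|---|---|---|
| 250 | 8.0% | 19.1% | 29.5% | 49.0% | 59.8% |
| 500 | 10.9% | 29.6% | 42.4% | 61.5% | 70.3% |
| 1,000 | 16.5% | 42.4% | 55.6% | 71.9% | 78.7% |

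**4. What stratification does.** If only the locations differ (20% versus 40%) and practices within a location do not, the error with m = 125 is 4.4%, so there is no inflation. Adding a within-location ICC of 0.01 brings it to 18%. If the listed ICC is a total and half of it lies between locations, the errors at m = 125 are 5.7%, 8.7%, 12.3%, 23.5% and 33.4%. If four-fifths does, they are 5.3%, 6.4%, 7.9%, 13.0% and 18.7%.

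**5. A version without an ICC.** Let the two practices in each location differ by a fixed gap centred on 30%, with m = 125. There are 2 × 2 = 4 possible allocations. In two of them both higher practices fall in the same arm; in the other two they offset. With 250 per arm, SE = √(2·0.3·0.7/250) = 0.041. A 10-point gap in the same arm therefore gives z = 0.10/0.041 = 2.44 and rejection of about Φ(2.44 − 1.96) = 68%.

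| Gap (points) | Same arm | Offsetting | Mean of four allocations |
|---|---|---|---|
| 2 | 7.7% | 4.8–5.0% | 6.3% |
| 4 | 16.3% | 4.8–5.0% | 10.6% |
| 6 | 30.9% | 4.8–5.0% | 17.8% |
| 8 | 49.7% | 4.8–5.0% | 27.3% |
| 10 | 68.6% | 4.8–5.0% | 36.7% |

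**The case against.** **The efficacy test already allows for clustering.** The mixed model is named in the very next sentence, and no decision rule depends on the chi-square. A simple comparison followed by the model that carries inference is a natural reading. This stands, and it keeps the point narrow. It does not make the chi-square valid: the sentence plans a test, does not label it, and concerns the same outcome.

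**The practices are comparable and the design is stratified.** Similar demographics may shrink within-location differences, but similar demographics do not mean equal vaccination rates. Stratification deals only with North against South.

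**The size rests on assumptions.** True. At an ICC of 0.001 or a 2-point gap the error is only about 6%. With four-fifths of the ICC between locations it stays at 5–8% up to a total ICC of 0.01. Against that, the outcome covers all eligible children at large practices, so 125 may be low.

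**The comparison may not be between arms.** The phrase about level of intervention could mean degree of exposure, since section C5 plans to count families using each component. Intervention and control practice are the only levels the design defines, so the arm reading is likelier. Under the other reading independence would still be ignored, but the figures above would not apply.

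**The mixed model may not be a safe fallback with four practices.** This is real. The plan does not specify the fitting. Assuming a practice random intercept, maximum likelihood, a Wald z test and no location term, at 125 per practice, simulation gives null rejection of about 11%, 14–15%, 21–25% and 31–32% at ICCs of 0.005, 0.01, 0.028 and 0.05. So dropping the chi-square does not by itself restore 5%. That is a separate problem with the model's reference distribution and does not rescue the chi-square.

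**Conclusion.** The concern holds. As written, the plan applies an individual-level test to a comparison randomised by practice, and its p-values are too small whenever the two practices within a location differ for reasons other than the intervention. The direction is certain under that condition. The size is not, because it depends on an ICC and practice sizes that the documents do not give. With 30% vaccinated, no effect and 125 children per practice, the error runs from about 6% to 47% over within-location ICCs of 0.001 to 0.05. It is lower if much of the variation lies between locations and higher with larger practices. The flaw concerns the chi-square p-values and does not change the mixed-model efficacy test, whose own small-sample behaviour is not endorsed here. It should be corrected, and the correction is small.

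**What to change.** Replace the chi-square sentence in section C4, Aim 3, Analyses with:

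> Vaccination proportions will be reported descriptively by arm and by practice; between-arm inference will come only from the analysis that accounts for practice randomisation.

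This changes one sentence and has no data or staff cost. The proportions are still reported; only the simple unadjusted p-values are lost.

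The change also makes plain how little between-arm inference four practices can support. For 30% versus 60% with 125 per practice, a practice-level t-test has about 68% power at ICC 0.01 with 2 degrees of freedom (if locations do not differ), or 29% with 1 degree of freedom when paired by location. At ICC 0.028 these fall to 45% and 21%. With four possible allocations, the smallest two-sided randomisation p-value is 2/4 = 0.5. Those limits come from the number of practices, not from this change. The reference distribution for the mixed model needs its own decision and is not settled by this sentence.
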